## **8.7. Severity Assessment**

Investigators will use the following definitions of Severity in accordance with the appropriate Common Terminology Criteria (CTCAE) term for Adverse Events (Version 4.0, Publish Date: October 1, 2009, (<http://ctep.cancer.gov/reporting/ctc.html>) to describe the maximum intensity of the adverse event. If the event is serious, the CTCAE grade reported in the adverse event CRF must be consistent with the description of CTCAE grade included in the narrative section of the serious adverse event (SAE) report.

**NOTE: The highlighted text above is not standard template language; please ensure Safety Risk Lead (SRL) has approved language and document on Study Decision Log.**

GRADE	Clinical Description of Severity
0	No Change from Normal or Reference Range (This grade is not included in the v 4.0 document but may be used in certain circumstances.)
1	MILD Adverse Event
2	MODERATE Adverse Event
3	SEVERE Adverse Event
4	LIFE-THREATENING OR DISABLING Adverse Event
5	DEATH RELATED TO Adverse Event

Note the distinction between the severity and the seriousness of an adverse event. A severe event is not necessarily a serious event. For example, a headache may be severe (interferes significantly with patient's usual function) but would not be classified as serious unless it met one of the criteria for serious adverse events, listed above.

### **8.8. Causality Assessment**

The investigator's assessment of causality must be provided for all adverse events (serious and non-serious); the investigator must record the causal relationship in the CRF, as appropriate, and report such an assessment in accordance with the serious adverse reporting requirements if applicable. An investigator's causality assessment is the determination of whether there exists a reasonable possibility that the investigational product caused or contributed to an adverse event; generally the facts (evidence) or arguments to suggest a causal relationship should be provided. If the investigator does not know whether or not the investigational product caused the event, then the event will be handled as "related to investigational product" for reporting purposes, as defined by the Sponsor (see Section on [Reporting Requirements](#)). If the investigator's causality assessment is "unknown but not related to investigational product", this should be clearly documented on study records.

In addition, if the investigator determines a serious adverse event is associated with study procedures, the investigator must record this causal relationship in the source documents and CRF, as appropriate, and report such an assessment in accordance with the serious adverse event reporting requirements, if applicable.

### **8.9. Exposure During Pregnancy**

For both unapproved/unlicensed products and for marked products, an exposure during pregnancy (also referred to as exposure in-utero [EIU] occurs if:

1. A female becomes, or is found to be, pregnant either while receiving or being exposed (eg, because of treatment or environmental exposure) to the investigational product; or the female becomes or is found to be pregnant after discontinuing and/or being exposed to the investigational product;

An example of environmental exposure would be a case involving direct contact with a Pfizer product in a pregnant woman (eg, a nurse reports that she is pregnant and has been exposed to chemotherapeutic products).

2. A male has been exposed (eg, due to treatment or environmental exposure) to the investigational product prior to or around the time of conception or is exposed during his partner's pregnancy.

If a study patient or study patient's partner becomes or is found to be pregnant during the study patient's treatment with the investigational product, the investigator must submit this information to Pfizer on an EIU Form (this is a specific version of the Serious Adverse Event Form). In addition, the investigator must submit information regarding environmental exposure to a Pfizer product in a pregnant woman (eg, a patient reports that she is pregnant and has been exposed to a cytotoxic product by inhalation or spillage) using the EIU Form. This must be done irrespective of whether an adverse event has occurred and within 24 hours of awareness of the exposure. The information submitted should include the anticipated date of delivery (see below for information related to termination of pregnancy).

Follow-up is conducted to obtain pregnancy outcome information on all EIU reports with an unknown outcome. The investigator will follow the pregnancy until completion or until pregnancy termination) and notify Pfizer of the outcome as a follow up to the initial EIU Form. In the case of a live birth, the structural integrity of the neonate can be assessed at the time of birth. In the event of a termination, the reason(s) for termination should be specified and, if clinically possible, the structural integrity of the terminated fetus should be assessed by gross visual inspection (unless pre-procedure test findings are conclusive for a congenital anomaly and the findings are reported).

If the outcome of the pregnancy meets the criteria for an SAE (ie, ectopic pregnancy, spontaneous abortion, intrauterine fetal demise, neonatal death, or congenital anomaly [in a live born, a terminated fetus, an intrauterine fetal demise, or a neonatal death]), the investigator should follow the procedures for reporting serious adverse events.

Additional information about pregnancy outcomes that are reported as serious adverse events follows:

- Spontaneous abortion includes miscarriage and missed abortion;
- Neonatal deaths that occur within 1 month of birth should be reported, without regard to causality, as serious adverse events. In addition, any infant deaths after 1 month should be reported as serious adverse events when the investigator assesses the neonatal death as related or possibly related to exposure to investigational product.

Additional information regarding the exposure during pregnancy may be requested by the investigator. Further follow-up of birth outcomes will be handled on a case-by-case basis (eg, follow-up on preterm infants to identify developmental delays). In the case of paternal exposure, the investigator will provide the study patient with the EIU Pregnant Partner Release of Information Form to deliver to his partner. The Investigator must document on the EIU Form that the patient was given this letter to provide to his partner.

## **8.10. Occupational Exposure**

An occupational exposure occurs when, during the performance of job duties, a person (whether a healthcare professional or otherwise) gets in unplanned direct contact with the product, which may or may not lead to the occurrence of an AE.

An occupational exposure is reported to the drug safety unit within 24 hours of the investigator's awareness, using the SAE report form, regardless of whether there is an associated AE/SAE. Since the information does not pertain to a subject enrolled in the study, the information is not reported on a CRF; however, a copy of the completed SAE report form is maintained in the investigator site file.

## **8.11. Withdrawal Due to Adverse Events (See Also [Section 6.4 Patient Withdrawal](#))**

Withdrawal due to AE should be distinguished from withdrawal due to other causes, according to the definition of AE noted earlier, and recorded on the appropriate AE CRF page.

When a patient withdraws due to a serious adverse event, the serious adverse event must be reported in accordance with the reporting requirements defined below.

## **8.12. Eliciting Adverse Event Information**

The investigator is to report all directly observed adverse events and all adverse events spontaneously reported by the study patient. In addition, each study patient will be questioned about adverse events.

## **8.13. Reporting Requirements**

Each adverse event is to be assessed to determine if it meets the criteria for serious adverse events. If a serious adverse event occurs, expedited reporting will follow local and international regulations, as appropriate.

### **8.13.1. Serious Adverse Event Reporting Requirements**

If a serious adverse event occurs, Pfizer is to be notified within 24 hours of investigator awareness of the event. In particular, if the serious adverse event is fatal or life-threatening, notification to Pfizer must be made immediately, irrespective of the extent of available adverse event information. This timeframe also applies to additional new information (follow-up) on previously forwarded serious adverse event reports as well as to the initial and follow-up reporting of exposure during pregnancy, exposure via breastfeeding cases, and occupational exposure cases.

In the rare event that the investigator does not become aware of the occurrence of a serious adverse event immediately (eg, if an outpatient study patient initially seeks treatment elsewhere), the investigator is to report the event within 24 hours after learning of it and document the time of his/her first awareness of the adverse event.

For all serious adverse events, the investigator is obligated to pursue and provide information to Pfizer in accordance with the timeframes for reporting specified above. In addition, an investigator may be requested by Pfizer to obtain specific additional follow-up information in an expedited fashion. This information collected for serious adverse events is more detailed than that captured on the adverse event case report form. In general, this will include a description of the adverse event in sufficient detail to allow for a complete medical assessment of the case and independent determination of possible causality. Information on other possible causes of the event, such as concomitant medications and illnesses must be provided. In the case of a patient death, a summary of available autopsy findings must be submitted as soon as possible to Pfizer or its designated representative.

### **8.13.2. Non-Serious Adverse Event Reporting Requirements**

All adverse events will be reported on the adverse event page(s) of the CRF. It should be noted that the form for collection of serious adverse event information is not the same as the adverse event CRF. Where the same data are collected, the forms must be completed in a consistent manner. For example, the same adverse event term should be used on both forms. Adverse events should be reported using concise medical terminology on the CRFs as well as on the form for collection of serious adverse event information.

### **8.13.3. Sponsor's Reporting Requirements to Regulatory Authorities**

Adverse event reporting, including suspected serious unexpected adverse reactions, will be carried out in accordance with applicable local regulations. In this clinical trial, the reference document for determining whether an event is unexpected is the Investigator's Brochure.

## **9. DATA ANALYSIS/STATISTICAL METHODS**

The detailed methodology for summary and statistical analysis of the data collected in this study will be documented in a Statistical Analysis Plan, which will be maintained by the sponsor. This document may modify the plans outline in the protocol; however, any major modifications of the primary endpoint definition and/or its analysis will also be reflected in a protocol amendment.

The following patient populations will be used in this study:

Full Analysis population: Full Analysis (or intent-to-treat) population will include all enrolled patients regardless of what treatment, if any, was received.

Per Protocol (PP) population: Per Protocol (or as-treated) population will include all enrolled patients who receive at least one dose of study drug.

The efficacy analysis will be based on the full analysis population. The pharmacokinetic analysis and safety analysis will be based on per protocol population.

## **9.1. Sample Size Determination**

Due to the rarity of the disease and the difficulties in identifying pediatric patient suitable for participation in this study only 6 patients will be included. The statistical power has not been calculated. Descriptive analysis approach will be adopted to report study results.

## **9.2. Analysis of Primary Endpoint**

Descriptive statistics for observed and dose-corrected (where appropriate) PK data will be reported for all patients with at least one PK observation by presenting the population size, arithmetic mean, standard deviation, percent coefficient of variation (CV%), median, minimum, maximum values. In addition, geometric mean and the 95% CI for the geometric mean, will be reported where appropriate. The key PK parameters in pediatric patients will be compared to adult patients with GIST based on historical data if data allows. The formal comparison will be carried out as part of the NONMEM portion using the historical PK data in adult GIST patients if data allows.

## **9.3. Efficacy Analysis**

Efficacy analysis will be performed using full analysis population, which includes all enrolled patients in the study. In addition, efficacy analysis may be performed on the subgroups of patients aged 6 years to less than 18 years, patients aged 18 years to less than 21 years.

### **9.3.1. Objective Response Rate**

Objective response rate (ORR) is defined as the proportion of patients with a confirmed complete (CR) or partial response (PR) relative to the number of patients enrolled in the treatment group. The number and percent of patients achieving objective response (CR or PR) will be summarized along with the corresponding exact 2-sided 95% CI calculated and presented.

### **9.3.2. Progression-Free Survival**

Progression-free survival (PFS) is defined as the time from the date of enrollment to the date of the first documentation of objective tumor progression or death due to any cause, whichever occurs first. PFS data will be censored on the day following the date of the last tumor assessment documenting absence of progressive disease for patients who 1) are given anti-tumor treatment other than the study treatment prior to observing objective tumor progression; 2) are removed from the study prior to documentation of objective tumor progression; 3) are ongoing at the time of the analysis.

Patients who do not have any post-baseline tumor assessments will have their PFS endpoint censored on the date of enrollment. Death or disease progression that occurs after more than one missed visit will be censored on the day following the date of the last tumor assessment as well.

PFS will be summarized using Kaplan-Meier methods and displayed graphically where appropriate. Median PFS and its corresponding 2-sided 95% CI for the median will be provided.

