##### **7.4.1. Time-To Event Endpoints**

For the purposes of endpoint definitions, the term “on-study” includes the period of study medication treatment plus 28 days following the last dose of study medication.

Progression-free survival (PFS) is defined as the time from the date of enrollment to the date of the first documentation of objective tumor progression.

PFS will be censored on the date of the last on-study tumor assessment documenting absence of progressive disease for patients who are alive, on study and progression free at the time of the analysis, are given antitumor treatment other than study treatment or are removed from treatment prior to documentation of disease progression or death on study. For PFS, patients having no tumor assessments after screening will have tumor related endpoints censored on the date of enrollment. Other censoring situations will be described in detail in the statistical analysis plan (SAP), for each endpoint analyzed.

Overall Survival (OS) is defined as the time from the date of enrollment to the date of death due to any cause. For patients still alive at the time of analysis, the OS time will be censored on the last date the patients were known to be alive. Patients lacking data beyond enrollment will have their OS censored at date of enrollment.

The 2-year survival probability is defined as the probability of survival at 2 years after the date of enrollment based on the Kaplan-Meier estimate.

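### The PFS no-scan rule in Protocol 9.3.2 and SAP 9.1.2.2 makes no exception for a patient who dies before any post-baseline scan, although both sections count death as a PFS event

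*Protocol*

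**What the plan says.** **Definition.** Protocol 9.3.2 counts the earlier of "objective tumor progression or death due to any cause, whichever occurs first", measured from enrollment. SAP 9.1.2.2 has the same definition.

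**No-scan rule.** Protocol 9.3.2 says: "Patients who do not have any post-baseline tumor assessments will have their PFS endpoint censored on the date of enrollment". SAP 9.1.2.2 repeats the sentence. Protocol 7.4.1 has its own form: "For PFS, patients having no tumor assessments after screening will have tumor related endpoints censored on the date of enrollment". None of the three mentions a patient who has died.

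**Missed-visit rule.** The next sentence of 9.3.2 and of the SAP censors a death or progression that follows more than one missed visit. Neither document says whether a visit here is a clinic visit or a scheduled tumor assessment.

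**General rule.** SAP Section 8 applies the Section 9 censoring rules to efficacy observations that are not events.

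**Protocol 7.4.1 otherwise.** Its definition stops at progression: "Progression-free survival (PFS) is defined as the time from the date of enrollment to the date of the first documentation of objective tumor progression". Its censoring date is given as: "PFS will be censored on the date of the last on-study tumor assessment documenting absence of progressive disease". Protocol 9.3.2 says instead: "PFS data will be censored on the day following the date of the last tumor assessment documenting absence of progressive disease". Section 7.4.1 censors patients who "are removed from treatment prior to documentation of disease progression or death on study", whereas 9.3.2 speaks of removal from the study.

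**ORR.** Protocol 7.4.2 divides by enrolled patients with measurable disease. Protocol 9.3.1 divides by all enrolled, and SAP 9.1.2.1 has no measurable-disease restriction.

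**The concern.** A patient who dies before any follow-up scan has the worst possible PFS outcome. The definition makes that death an event on its own date. The no-scan sentence, taken at face value, removes the same patient from the risk set at time zero, so the death never lowers the curve. Two programmers could code the same patient differently, each with textual support.

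The error runs in one direction: literal use of the rule can only make early PFS look better. With about six children, a single patient carries roughly one sixth of the estimate. If the choice were made after the data are seen, it would also be open to the charge of being data-driven.

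**Working it through.** The plan states no figure for this point, so there is nothing to reproduce. The check is a comparison of texts followed by a small illustration.

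**1. Does any text settle the conflict?**
- Protocol Section 9 lets the SAP modify the protocol's analysis plans, and 7.4.1 refers other censoring situations to the SAP. The SAP repeats the no-scan rule unchanged, so precedence does not help.
- SAP Section 8 censors only observations without an event. As death is an event, this favours counting it.
- The missed-visit sentence in the same section censors some deaths outright. Section 9 therefore can override an event, and Section 8 alone is not decisive.

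**2. Which deaths are exposed?** A cycle is 42 days (Protocol 5.2.3). Scans fall within 14 days before the end of each even-numbered cycle (Protocol 7.4; Table 1, footnote 14).
- End of Cycle 2: 2 × 42 = day 84. Window: 84 − 14 = day 70 to day 84.
- End of Cycle 4: 4 × 42 = day 168. Window: 168 − 14 = day 154 to day 168.

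This assumes no cycle delays and enrollment close to the first dose. Imaging is also due when progression is suspected and at the end of treatment, so not every death before day 84 would be unscanned.

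**3. Size.** Inputs from the documents: 6 children (Protocol 9.1) and up to 15 young adults (Protocol 3), at most 6 + 15 = 21 patients. Assumed: one death on day 50 with no post-baseline scan, and all others event-free and under observation then. The Kaplan-Meier step at an event is S = 1 − d/r, with d events among r at risk.

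| Handling of the death | n = 6 | n = 21 |
|---|---|---|
| Censored at day 0 (literal reading) | no event; S = 100% | no event; S = 100% |
| Event on day 50 | 1 − 1/6 = 5/6 = 83.3% | 1 − 1/21 = 20/21 = 95.2% |

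**4. The median.** In step 3 the curve stays above 50% under either handling, so the median is not reached. It moves only if further events are assumed. Take 6 patients, an unscanned death on day 40, and progressions on days 84, 168, 252, 336 and 420.
- Death counted: S = 5/6, 4/6, 3/6 at days 40, 84, 168. Median day 168.
- Death censored at day 0: S = 4/5, 3/5, 2/5 at days 84, 168, 252. Median day 252.

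**5. The other differences in 7.4.** On definition, censoring date and removal rule, SAP 9.1.2.2 matches 9.3.2 each time, so one rule will be run. The censoring dates differ by one day for the same last scan. On ORR, the SAP follows 9.3.1 in applying no measurable-disease restriction.

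**The case against.** The best defence is that the SAP should be read as a whole. Section 8 confines censoring to non-events, 9.1.2.2 makes death an event, and the missed-visit sentence says specifically when a death is censored. On that reading other deaths count, and the no-scan sentence covers only patients without an event. This is the more natural reading, and it stands as the probable intent. It is still inference: the no-scan sentence is unqualified in three places.

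The practical exposure is also small. Protocol 1.1 describes an indolent course in children. Overall survival counts every death, and SAP 9.1.3.1 lists deaths, so an early death would stay visible. SAP Section 9 runs time-to-event analyses only if there are enough events. With one event the planned summary, the median, would not be reached. All of this holds and limits the weight of the point.

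A reader might infer more from Section 7.4, in three ways that the documents do not support.
- **That PFS here is really time to progression.** The 7.4.1 definition omits death, but its own censoring clause refers to death on study, and 9.3.2 and the SAP include death. This looks like a drafting omission.
- **That the two removal rules will give different results.** Leaving treatment is not leaving the study (Protocol 6.4), and 7.4.1 limits the on-study period, which "includes the period of study medication treatment plus 28 days following the last dose of study medication". But the SAP follows 9.3.2. Whether a later death would count under 9.3.2 also depends on what *visit* means: if clinic visits are meant, such a death may be censored there too.
- **That the ORR denominator is unsettled.** Only 7.4.2 adds the measurable-disease restriction. The Amendment 2 rationale also cites an absence of PR or CR; if that holds, ORR is 0% on either denominator.

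The SAP was written for a protocol dated 17 June 2011. That does not change this point, since its PFS text matches the current 9.3.2.

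**Conclusion.** The point holds as a minor defect of wording. The no-scan rule, as literally written, contradicts the PFS definition in the same section, and no other text resolves the conflict. If applied literally to one unscanned early death, it would raise early PFS from 83.3% to 100% with 6 patients, or from 95.2% to 100% with 21. Those figures rest on an assumed death and no other event by then; no such death is documented. The median changes only if several more events occur.

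The documents do not show that the sponsor intends to censor such deaths, and a claim that PFS will be biased goes too far. The endpoint is secondary and descriptive, the analysis may not be run, and the primary PK result is untouched.

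**What to change.** **Main change (Protocol 9.3.2 and SAP 9.1.2.2).** State that a patient with no post-baseline tumor assessment is censored at enrollment unless the patient dies before the second scheduled tumor assessment (end of Cycle 4). In that case the death is an event on the date of death. Censoring for other anti-tumor treatment or removal from the study before death should apply as it does for scanned patients. State also that *visit* in the missed-visit rule means a scheduled tumor assessment. The Cycle 4 limit then agrees with that rule, because a patient who dies before it has missed at most one scheduled assessment.

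**Housekeeping (Protocol 7.4).** Replace the PFS definition, censoring date and removal rule in 7.4.1 with a cross-reference to 9.3.2. Align the ORR denominator in 7.4.2 to all enrolled, as in 9.3.1.

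**Cost.** Wording only, best settled before database lock. Deaths, new anti-cancer therapy and survival follow-up are already collected (Protocol 6.3.2), so no new data are needed. The one downside is that PFS may come out slightly less favourable.
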